Aim 1. Measure impact of apps on access to dermatology care. *San Francisco VA Health Care System's involvement is limited in Aim 1. All data related to this aim is collected by the VA's Center for Access Policy, Evaluation Research (CAPER) located at the Boston VA Health Care System. All data collected from the Corporate Data Warehouse, or any other databases as approved by the Boston VA Health Care System IRB will be anonymously recorded, aggregated, and shared with investigators and study staff at the San Francisco VA Health Care System and other sites. No analysis of the primary data will occur at San Francisco VA.*

Both apps will be made available over a 2 year period in a randomized, stepped-wedge design to Veterans Health Administration (VHA) facilities, after each app becomes available. The *VA Telederm* app will be distributed to 36 eligible VHA facilities that currently have low teledermatology activity and thus have had relatively poor adoption of basic consultative teledermatology. The *My Telederm* app will be distributed to 24 facilities with dermatology clinics that currently have relatively high teledermatology activity and thus already have relatively mature teledermatology programs ready for advanced operations.

By using health factors and stop codes unique to each app, we will use the VA Corporate Data Warehouse (CDW) to measure the impact of both apps on the following outcomes reflecting dermatology access: 1) Consult and appointment completion times for both teledermatology and in-person consults, stratified by new and established patients (primary outcome); 2) Instances of

dermatologic care (associated with either teledermatology or in-person dermatology encounters); and 3) Travel costs for VA, as well as non-VA care consult rates and associated costs. In addition, the following outcomes will be measured specifically for the *My Telederm* app: 1) Proportions of new patient encounters in-person dermatology clinics; and 2) “No-show” rates and timeliness of follow-up. Results of each of these access measures will be stratified to examine the effect on rural/highly rural Veterans, as well as to determine whether a differential effect occurs for facilities with some pre-existing teledermatology relative to those that had none.

Aim 2. Determine the factors that affect personal and organizational adoption of mobile apps.

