Using the Replicating Effective Programs framework, we will work with OCC to implement and measure the deployment, adoption and utilization of both teledermatology apps throughout all eligible VA sites. In one sub-aim, which is the principal focus of the current IRB application, we will conduct a formative evaluation of the implementation process at 3 early adopter sites to develop implementation strategies to guide subsequent nationwide deployment and research. Surveys and semi-structured interviews will assess Organizational Readiness for Change (ORC) at these sites regarding the apps, and link ORC to stages of implementation, barriers and facilitators to implementation, and implementation effectiveness as measured by uptake of the apps and actual use of teledermatology.

In the second sub-aim, we will also monitor deployment, adoption and utilization of both teledermatology apps nationally by analyzing remotely accessible data from the CDW and OCC. The primary data will be collected by CAPER under its own IRB approval, and aggregate data will be shared with the PIs and co-investigators. We will then correlate the degree of adoption with reach of the program (i.e., number of Veterans served) and stratify analyses of primary outcomes from Aim 1 based on degree of adoption.

At the conclusion of the project, we expect to document important indicators of mobile teledermatology’s effects on patient access in the nation’s largest healthcare system and to comprehensively understand the implementation of mobile teledermatology. These novel achievements will guide future mobile telemedicine endeavors in VA, and will inform other large healthcare organizations interested in telehealth.

8.3 DESIGN: Briefly describe the study design (e.g., observational, interventional, randomized, placebo-controlled, blinded, cross-over, cross-sectional, longitudinal, pharmacokinetic, etc.):

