3. Dermatology Clinical Champions
4. Imaging Master Preceptors
5. Clinical Applications Coordinators (CACs)
6. Teledermatology Readers

Additionally, the three sites will identify **other staff** whose work or clinical decision-making may change as a result of app implementation. These individuals are:

1. Primary Care Clinicians
2. Telehealth Clinical Technicians/Telehealth Imagers
3. Dermatology Clinicians
4. Other staff at the three early adopter sites whose work may be affected by teledermatology.

Detailed description of formative evaluation

The Principal Investigators will be asked to complete and provide San Francisco VA HCS research staff with a baseline site information document for each of the early adopter sites. This document will be used to identify core implementation team members and other staff involved in teledermatology and their relationships among each other, as well as teledermatology processes, size and composition of each medical centers, and impacted clinical services. We may supplement this information by examining organizational-level information (e.g., number of patients, number of providers) that is normally available to all VA employees through the VHA Reports and Measures Portal (RAMP) and/or VHA Report Services Center (VSSC).

Upon completion of the baseline site information document, the following specific steps will be overseen by the San Francisco VA Health Care system research staff.

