 2. Using the semi-structured interview methods above, each core implementation team member, director of primary care, Chief of Dermatology, FTC, imager, and other staff members participating in processing or supporting teledermatology at each site will be interviewed. The sustainability interview will explore in more depth the areas surveyed in the PSI (Leadership, Collaboration, Demonstrating Program Results, Funding, and Program Responsivity). We have previously used the combination of PSI and qualitative interviews to evaluate the sustainability of a multi-facility program for the Office of Patient Centered Care and Cultural Transformation. This program sustainability interview guide will be introduced by the telephone consent script attached to this application.

Sub-Aim 2.2

Implementation of field sites will also be assessed at all participating sites by monitoring intermediate milestones and quantitative indicators of implementation that are available in CDW as well as from OCC's own telehealth database and Web and Mobile Solutions (WMS) device procurement program.

To understand how rapidly sites meet key milestones as a result of the OCC implementation process, and if the apps are more effective among sites that have reached more implementation milestones, randomized sites will be asked to complete a bi-monthly implementation site report monitoring key milestones, collected electronically via REDCAP on the VA intranet. This bi-monthly report is based on the bi-monthly site report utilized as part of the formative evaluation described above. Sites will be sent email reminders two weeks and one week prior to, and one week after the due date, with follow up via phone call, if necessary. Four of these randomized sites will be recruited to participate in semi-structured sustainability interviews using the same guides used in the formative evaluation and will be introduced by the telephone consent script attached to this application. These Interview data will be collected by

recording phone conversations directly onto secure VA networked servers or encrypted computers, using MS Teams and Phillips recorder.

8.11 INSTRUMENTS: List all questionnaires, surveys, interview, or focus group guides that will be used for this study:

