In the third phase, we will apply the same criteria across the cases to determine if cross-case variation in implementation is consistent with the hypothesized relationships in the model. Consistent with the organization-level focus of the model, we will aggregate and analyze quantitative data on implementation policies and practices (e.g. staffing levels) and other study constructs using simple statistics. In addition, we will create within-case and between-case data displays that cross-tabulate the quantitative and qualitative data in order to facilitate the use of pattern-matching logic.

Sub-Aim 2.2: Collection of this data will be descriptively summarized to understand how rapidly sites meet key milestones as a result of the OCC implementation process, correlate the milestones to the number of patients serviced via the apps (i.e., reach), and allow for stratified analyses of main quantitative study results by degree of implementation based on reaching milestones to determine if the apps are more effective among sites that have reached more implementation milestones. We will analyze the qualitative data from the interviews in the same manner as described above for the formative evaluations using direct content analysis to examine themes within each case and to determine cross-case variation.

8.14 REFERENCES: List only the 5-10 most relevant references (a separate bibliography can be attached for reference purposes if this study involves novel approaches, agents, or an emerging technology that the IRB may not be familiar with):

1. Landow, S.M., D.H. Oh, and M.A. Weinstock, *Teledermatology within the Veterans Health Administration, 2002-2014*. *Telemed E Health*, 2015. **21**(10): p. 769-773.
2. Kilbourne, A.M., M.S. Neumann, H.A. Pincus, et al., *Implementing evidence-based interventions in health care: application of the replicating effective programs framework*. *Implement. Sci.*, 2007. **2**: p. 42.

3. Neumann, M.S. and E.D. Sogolow, *Replicating effective programs: HIV/AIDS prevention technology transfer*. AIDS Educ. Prev., 2000. **12**(5 Suppl.): p. 35-48.
4. Moullin, J.C., D. Sabater-Hernandez, F. Fernandez-Llimos, et al., *A systematic review of implementation frameworks of innovations in healthcare and resulting generic implementation*. Health Res. Policy Syst., 2015. **13**: p. 16.
5. Klein, K. and J. Sorra, *The challenge of innovation implementation*. Academy of. Management Review, 1996. **4**: p. 1055-1080.

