10.0 Sample Size and Eligibility Criteria

10.1 ENROLLMENT TARGET: How many people will you enroll:

50

If there are multiple participant groups, indicate how many people will be in each group:

Aim 1 will collect aggregate data relating to access exclusively by Veteran patients to VHA dermatology. While some characteristics such as Veteran patient rurality and location will be monitored for individual encounters, the research has no direct or indirect patient contact or involvement. Our randomized study of a total of 60 nationally distributed VA facilities will include encounter data from Veteran patients who are expected to generally reflect the diversity of VA's patient population with respect to age, gender, race and ethnicity. Children will be excluded since VHA does not serve pediatric populations and since children are not a target population for the apps.

Aim 2, as part of formative evaluation, will involve structured interviews and surveys of VHA staff at three early adopter sites, including VISN and facility organizational leadership (VISN Telehealth Leads, Dermatology Chiefs, Facility Telehealth Coordinators), support staff (Information Security Officers, Clinical Application Coordinators, Information Technology specialists), and clinical end-users (primary care providers, Telehealth Clinical Technicians, dermatologists) and clinical support staff (Medical Support Assistants). Thus we anticipate 16-17 subjects will participate at each site. Since there are 3 sites that will participate in the formative evaluation, we estimate that 50 subjects will participate via surveys and interviews overall. For the formative evaluation, some but not all subjects may be Veterans, and will

reflect the composition and diversity of VHA's workforce. For sub aim 2.2, 28 site leads will receive the bi-monthly report and 4 of these 28 sites will be asked to participate in a semi-structured interview. Two will have high usage of the app and two with low to no usage of the app.

10.2 TOTAL PARTICIPANTS: For multicenter studies, how many people will be enrolled in total:

50

10.3 SAMPLE SIZE JUSTIFICATION: Explain how and why the number of people was chosen. For multi-site studies, this is referring to the number that will be enrolled across all sites:

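### Reach is a raw count of Veterans served, correlated across facilities with adoption and milestones without scaling for facility size, so the correlation may partly reflect size.

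*Combined protocol and SAP*

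**What the plan says.** Reach is defined twice, both times as an unscaled number. Section 8.2 will "correlate the degree of adoption with reach of the program (i.e., number of Veterans served"). Section 8.13, under Sub-Aim 2.2, will "correlate the milestones to the number of patients serviced via the apps (i.e., reach").

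Section 8.13 presents the work as descriptive: "Collection of this data will be descriptively summarized to understand how rapidly sites meet key milestones". It gives no test, significance level or decision rule for these correlations, and no denominator, offset, partial correlation or stratification by facility size.

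Degree of adoption is not defined as either a count or a proportion. Besides the bi-monthly milestone report, section 8.9 (Sub-Aim 2.2) names these sources: "quantitative indicators of implementation that are available in CDW as well as from OCC's own telehealth database and Web and Mobile Solutions (WMS) device procurement".

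Size data appear in section 8.9 only as an optional supplement to the baseline description of the three early adopter sites ("organizational-level information (e.g., number of patients, number of providers")). Those sites are outside the randomised study.

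On the number of sites, section 10.1 says "28 site leads will receive the bi-monthly report", against 36 plus 24, or 60, facilities planned in section 8.2.

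**The concern.** The number of Veterans served through an app is facility volume multiplied by rate of use. Two facilities with the same rate but different volumes have different reach under this definition. A large site with slight uptake can also rank above a small site that moved most of its patients to the app.

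If the other variable also rises with size, the two correlate even when adoption or milestones have no relation to the rate of use. The result could then be read as evidence that completing milestones extends reach. Section 8.2 says the findings should guide later telemedicine programmes in VA and inform other organisations, so that reading would matter.

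The plan scales for size elsewhere. Site eligibility (sections 8.5 and 10.3) uses teledermatology as a percentage of all dermatology encounters, and several Aim 1 outcomes in section 8.2 are rates or proportions.

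**Working it through.** The plan states no expected correlation, so there is no figure to reproduce. The check asks how large a correlation size alone could produce.

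**Inputs from the documents.** Reach is a count (8.2, 8.13); 28 sites receive the milestone report (10.1); some sites are expected to have low or no use (10.1).

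**Assumptions, shown as ranges.** Facility size and rate of use are log-normal. The log-SD of size, s, is 0.3 or 0.8, and the log-SD of the use rate, u, is 0.5 or 0.8. The use rate is unrelated to size and to milestones. Milestones correlate k = 0, 0.3 or 0.5 with log size.

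**Formula.** log(count) = log(size) + log(rate). With no true link between milestones and rate, the correlation of milestones with log(count) is

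r = k × s / √(s² + u²),

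and under normality the rank correlation is (6/π) × arcsin(r/2). For s = 0.8, u = 0.5, k = 0.5: √(0.64 + 0.25) = 0.943, r = 0.5 × 0.8/0.943 = 0.424, rank correlation 0.41. Simulated means for 28 sites (8,000 sets per row) are slightly lower, as expected in a small sample.

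| s | u | k | r | rank, formula | rank, simulated |
|---|---|---|---|---|---|
| 0.3 | 0.8 | 0.3 | 0.105 | 0.10 | 0.10 |
| 0.3 | 0.8 | 0.5 | 0.176 | 0.17 | 0.16 |
| 0.3 | 0.5 | 0.3 | 0.154 | 0.15 | 0.14 |
| 0.3 | 0.5 | 0.5 | 0.257 | 0.25 | 0.23 |
| 0.8 | 0.8 | 0.3 | 0.212 | 0.20 | 0.19 |
| 0.8 | 0.8 | 0.5 | 0.354 | 0.34 | 0.33 |
| 0.8 | 0.5 | 0.3 | 0.254 | 0.24 | 0.23 |
| 0.8 | 0.5 | 0.5 | 0.424 | 0.41 | 0.40 |

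With k = 0, r = 0 in every case. With reach as a rate, the simulated mean is about 0 in every row.

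**Half the sites with no use, independent of size.** At s = 0.8 and u = 0.8 the simulated mean falls to about 0.05 (k = 0.3) and just over 0.08 (k = 0.5). At u = 0.5 the upper value is about 0.10.

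**Adoption as a count of users or devices.** Here both variables contain size. With 28 sites, u = 0.5, and the share of potential users adopting unrelated to the use rate, the simulated mean rank correlation is 0.19, 0.46 and 0.65 for s = 0.3, 0.6 and 0.9. Runs with 24, 36 and 60 sites give similar means. Scaling both variables returns the mean to about 0.

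**Noise when milestones are unrelated to size.** A true correlation of milestones with log rate is multiplied by u / √(s² + u²) when the count is used. For s = 0.8 this factor is 0.5/0.943 = 0.53 or 0.8/1.131 = 0.71, so a true 0.5 appears as about 0.27 to 0.35.

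**Scale.** The sampling SD of a rank correlation near zero with 28 sites is about 1/√27 = 0.19. The spurious component therefore runs from about half of one SD to about two.

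**The case against.** The strongest objection is that no document links facility size to milestones. Section 8.13 describes milestones as resulting from a centrally run rollout, and section 8.9 names a central device programme. If completion does not depend on size, nothing spurious arises. This stands. A reader might infer that size alone is bound to produce the association; the documents do not support that for milestones. The link is automatic only if adoption is a count, which the plan leaves open.

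Second, no hypothesis test is planned. A reader might want to quote a false-positive rate, but that would describe an analysis the plan does not contain. This also stands, so the size of the effect is given here as a shift in the coefficient.

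Third, inputs such as a wide spread of facility size and use at every site favour a large effect. Section 10.1 expects sites with little or no use, and section 8.13 reports poor site participation. This stands as a limit on magnitude and is why the range extends down to about 0.05.

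Fourth, a count is a legitimate quantity. Section 8.4 names expansion of the number of patients served as a knowledge gap. This supports reporting the count. It does not support using an unscaled count to judge, across facilities of different size, whether adoption or milestones go with greater reach.

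Finally, a denominator of consult requests in the same months as app use could rise with uptake and hide real growth, and established patients due for follow-up are not a listed Aim 1 measure. Both points stand and favour a pre-rollout denominator.

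**Conclusion.** The point holds in a conditional form. Both definitions of reach are raw counts, and no adjustment for size is planned. The correlations partly reflect size if adoption or milestones are related to it; otherwise size variation only weakens a real association.

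For milestones, the spurious rank correlation is about 0.10 to 0.40 for 28 sites, a log-SD of size of 0.3 to 0.8 and a milestone-size correlation of 0.3 to 0.5. It is about 0.05 to 0.08 if half the sites have no use (log-SD of size and of use rate both 0.8), and about 0 if milestones are unrelated to size. All of these inputs except the 28 sites are assumptions.

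A reader might infer that this threatens the trial's main result. It does not: the analysis is descriptive and secondary, and neither the randomised comparison nor the sample size depends on it. Nor does the statement in section 8.13 that the Aim 1 analysis could not be followed withdraw the Sub-Aim 2.2 correlations.

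**What to change.** Amend sections 8.2 and 8.13 along these lines: for each app, degree of adoption and milestones reached will be correlated with the number of Veterans served through the app per unit of the facility's pre-rollout dermatology volume; adoption will be scaled in the same way if it is a count; the raw number served will be reported alongside as total volume.

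FY2016 dermatology encounters are a ready denominator. They were already used to determine site eligibility, and the app cannot change them.

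The cost is about one sentence in each section and no new data collection. There is a small downside: rates at small sites are noisy, and the investigators must agree on the denominator. FY2016 encounters measure volume rather than eligible patients, so the result is a scaled rate and not a strict proportion reached.

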2. **Bi-monthly Monitoring of Implementation – Process of Implementation.** At the start of each app implementation, the research team will interview the core implementation team as a group during a conference call after obtaining verbal consent (the telephone consent script and Site Process Guide are attached to this application). Baseline information on the site's process of implementing each app and related clinical workflow will be collected through a series of questions based on expected workflow, such as identifying essential tasks in IT and informatics as well as staff training that need to occur. Additionally, we will collect baseline information on the organization of dermatology services, the referral process from PCPs, number of providers, and perceived volume of patients. Components of the workflow process will be stored in an Excel spreadsheet to be sent to the sites for updates every two months.
3. **Bi-monthly Monitoring of Implementation – Implementation Progress.** We will also measure the implementation process by bi-monthly site reports from the three sites. Implementation progress will be assessed utilizing the Stages of Implementation Completion (SIC). SIC enumerates key pre-implementation, implementation and sustainability milestones. Dates by which specific implementation milestones were reached will be identified. Bi-monthly (every other month) reports will also include assessment of barriers and facilitators identified through the ORC measurement process. Bi-monthly information will be fed back to project and OCC leadership so that program adjustments can be made. The Bi-Monthly Site Report survey is attached to this application.

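### Stratifying Aim 1 results by adoption or milestones is a non-randomised comparison and cannot show that the apps are more effective at well-implemented sites

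*Combined protocol and SAP*

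**What the plan says.** Three places describe the analysis.

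- Section 8.2, Aim 2, second sub-aim: the investigators will "stratify analyses of primary outcomes from Aim 1 based on degree of adoption".
- Section 8.9, Sub-Aim 2.2: one purpose of the site reports is to learn "if the apps are more effective among sites that have reached more implementation milestones".
- Section 8.13, Sub-Aim 2.2: the data are to allow "stratified analyses of main quantitative study results by degree of implementation based on reaching milestones", and the stated purpose is "to determine if the apps are more effective among sites that have reached more implementation milestones".

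The milestones are self-reported: "randomized sites will be asked to complete a bi-monthly implementation site report monitoring key milestones" (section 8.9). That report is based on the one used in the formative evaluation, where progress is scored with the Stages of Implementation Completion (SIC); "SIC enumerates key pre-implementation, implementation and sustainability milestones". Section 10.1 adds that "28 site leads will receive the bi-monthly report".

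Sections 8.2 and 8.3 randomise only when a site receives an app. VA Telederm goes to "36 eligible VHA facilities that currently have low teledermatology activity" and My Telederm to 24 others. Section 8.13 analyses Aim 1 with mixed models (period fixed effects, cluster random effects), an instrumental-variable estimate of the complier effect, and an intent-to-treat analysis. It opens by stating that the Aim 1 plan could not be followed because sites did not participate. It does not withdraw the stratification.

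**The concern.** Randomised release order protects the comparison of released with not-yet-released site-quarters. It does not protect a comparison of sites sorted by how well they took the app up.

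The protocol itself points to a possible common cause. Section 8.5 excludes sites without dermatologists as unlikely to be able to adopt, and section 8.13 expects administrative support and implementation to go together. The primary outcome includes completion times for in-person consults, which staffing can plausibly change without any app. A site that gains capacity after release may therefore both adopt more and shorten its waits.

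At stake is the meaning of one explanatory result. As worded, a larger change at high-milestone sites would be reported as greater effectiveness of the app there. The design cannot separate that from a change in the sites themselves.

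**Working it through.** The documents give no figure for this analysis, so there is none to reproduce. The check asks what the stratified comparison shows when the true app effect is zero.

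**Inputs from the documents:** 36 and 24 sites (8.2); three-month steps (8.3); 2.5 years, hence 10 quarters (8.13); a planning difference of 10% from baseline (10.3).

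**Assumptions:** the number of steps (9 of 4 sites, 8 of 3 sites), all variances, and all correlations between adoption and site capacity.

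**Check 1: size of the false gap (36 sites).** Site capacity moves waits with SD 10% and quarter-to-quarter correlation 0.7. Let Δ be a site's mean capacity after release minus before. The adoption score is r·z(Δ) + √(1 − r²)·noise, split at the median. Each stratum is fitted separately with site and period effects. The gap is the estimated effect in high adopters minus that in low adopters.

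| r | High adopters | Low adopters | Gap in size (points) | Gap with shared period effects |
|---|---|---|---|---|
| 0 | – | – | about 0 | – |
| 0.3 | −1.1% | +1.2% | 2.4 | 4.1 |
| 0.5 | −2.0% | +2.1% | 4.1 | 7.0 |

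The gaps come from unrounded effects. The unstratified effect stays near 0 throughout. Repeat runs gave gaps of 2.3 to 2.7 and 3.9 to 4.1.

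With separate strata, the SD of the gap across trials is about 3.9 (r = 0.3) and 3.8 (r = 0.5). For gap g and SD s, a two-sided 5% test that uses this SD rejects with probability Φ(g/s − 1.96) + Φ(−g/s − 1.96):

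- r = 0.3: g/s = 2.4/3.9 = 0.615, so Φ(−1.345) + Φ(−2.575) = 0.089 + 0.005 = 0.094.
- r = 0.5: g/s = 4.1/3.8 = 1.079, so Φ(−0.881) + Φ(−3.039) = 0.189 + 0.001 = 0.190.

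That is about 9% and 19% against a nominal 5%. The gaps equal 2.4/10 = 24% and 4.1/10 = 41% of the 10% planning difference.

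**Check 2: which mechanisms matter.** This uses a random-intercept model with period effects and 1,500 null trials per row. Assumed: site SD 1.0, quarter residual SD 0.5, site-trend SD 0.05 per quarter, and a capacity change of SD 0.5 at a random quarter. Entries are the percentage of trials with a false interaction.

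| Adoption related to | r | 36 sites, separate | 36 sites, shared | 24 sites, separate | 24 sites, shared |
|---|---|---|---|---|---|
| nothing | 0 | 4.6 | 5.2 | 4.9 | 4.9 |
| constant site level | 0.6 | 4.8 | 5.7 | 5.5 | 5.2 |
| time since release | 0.6 | 6.2 | 5.1 | 5.1 | 4.2 |
| site's linear trend | 0.3 | 5.9 | 22.0 | 6.5 | 18.1 |
| site's linear trend | 0.6 | 7.1 | 49.9 | 6.5 | 36.8 |
| site's capacity change | 0.3 | 7.9 | 27.6 | 8.8 | 22.0 |
| site's capacity change | 0.6 | 8.1 | 57.9 | 9.5 | 44.7 |

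Separate and shared refer to the period effects of the two strata. The intent-to-treat estimate was within 0.01 of zero in every row. With separate strata there is no mean bias when adoption follows only a linear trend, and a small one (0.03 to 0.05 in outcome units) when it follows a capacity change. The documents do not say whether strata would share period effects.

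**The case against.** The strongest reply is that the analysis may never exist. Section 8.13 says the Aim 1 plan was not followed and that work turned to factors in consult completion among app users. This stands as a limit on consequence. A reader might infer that rollout decisions would be misled; the documents do not support that, because they give no sign that the stratified result was produced. They do, however, leave the inference in three sections.

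Second, uptake is already handled in ways that use the randomisation, by the intent-to-treat and instrumental-variable analyses. This stands too. A reader might infer that the trial's main comparison is compromised; it is not. Neither analysis is the site-level milestone split, though, so neither repairs it.

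Third, every site supplies its own control quarters. This is right: constant differences between stronger and weaker sites give no bias. The false gap needs adoption to follow change within a site. Its sign is also assumed, since overloaded sites might adopt more and reverse it.

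Fourth, high adopters look better in about 73% and 86% of the null trials at r = 0.3 and 0.5. A reader might take these for false-positive rates. They count only the sign of the gap, for which chance gives 50%; the corresponding test error is about 9% and 19%.

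Fifth, SIC includes pre-implementation milestones, so not every milestone follows release. Those are still determined by the site. Also, 28 leads receive the report against 36 + 24 = 60 planned facilities, so the 36-site simulation represents the adoption split better than the milestone split. Incomplete reporting may add selection of its own.

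Finally, section 8.13 calls the Sub-Aim 2.2 summary descriptive, and section 8.2 already plans a split by pre-existing teledermatology. Both help, but the sentence that calls the data descriptive still ends in a conclusion about effectiveness.

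**Conclusion.** The point holds in a limited form. Adoption and milestones are site-driven, not randomised, and largely post-release, and the plan states a conclusion about app effectiveness from them without any caveat. If adoption tracks changes in a site's own capacity, a difference between strata can appear for an inert app.

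Under the assumptions of Check 1 with separate strata, the mean false gap is about 2.4 to 4 percentage points and the test error about 9% to 19%; shared period effects make the gap larger. These sizes rest on assumed variances, correlations and step counts. That the bias is possible does not depend on those particular values. The defect is confined to a secondary explanatory analysis and should be corrected in the text.

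**What to change.** In sections 8.2 (Aim 2, second sub-aim), 8.9 and 8.13 (Sub-Aim 2.2):

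1. State that the split by adoption or milestones is a descriptive, non-randomised association.
2. Replace the inference about greater effectiveness with wording such as *describe how outcomes vary with implementation*. Alternatively, withdraw the stratification, given the statement in 8.13 that the Aim 1 plan was not followed.
3. If Aim 1 effects are estimated, base any effect-modification claim on site factors fixed before release and already in hand (FY2016 teledermatology share, dermatologist FTE), fitted as interactions with release. This extends the split by pre-existing teledermatology in section 8.2. It adds to the descriptive milestone table and does not replace it, because it answers a different question.

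The cost is wording only, with no new data. The downside is that the milestone question gets a descriptive answer, not a causal one.
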